27 JAN 2021

regorafenib. The appropriate interval of time between minor procedure (biopsy) and regorafenib treatment required to minimize the risk of impaired wound healing and bleeding has not been determined. Treatment with regorafenib may be interrupted at least 24 hours before the procedure and the decision to reinitiate regorafenib treatment should be based upon a clinical assessment of satisfactory wound healing and recovery from the procedure.

6.5.3 **Prohibited Prior and Concomitant Therapies**

Patients are prohibited from receiving the following therapies during the course of the study:

- a) Disease-specific anti-neoplastic therapies, including kinase inhibitors, immunotherapy, chemotherapy, hormonal therapy, non-palliative radiation therapy or experimental therapies other than regorafenib and nivolumab are not allowed.
- b) Any botanical preparation (e.g., herbal supplements or traditional Chinese medicines) intended to treat the disease under study or provide supportive care. Use of marijuana and its derivatives for treatment of symptoms related to cancer or cancer treatment are permitted if obtained by medical prescription or if its use (even without a medical prescription) has been legalized locally.
- c) Surgery for symptom management or tumor control.
- d) Concomitant use of strong inhibitors of CYP3A4 and strong inducers of CYP3A4 (listed in Section 10.8) are not permitted for 2 weeks prior to start of study intervention or during the study.
- e) Grapefruit and grapefruit juice (CYP3A4 inhibitor) consumption is not permitted during the study.
- f) Excessive intake of biotin above the recommended daily dose of 30 μg. Biotin is found in multivitamins, including prenatal multivitamins, biotin supplements, and dietary supplements for hair, skin, and nail growth at levels that may interfere with laboratory tests.
- g) Investigational anti-neoplastic chemo/hormonal/immunotherapy.
- h) Any live/attenuated vaccine (e.g., varicella, zoster, yellow fever, rotavirus, oral polio and measles, mumps, rubella [MMR]) during treatment and until 100 days post last dose (LD) of nivolumab. Seasonal influenza vaccines for injection are generally killed virus vaccines and are allowed; however intranasal influenza vaccines (e.g., FluMist[®]) are live attenuated vaccines and are not allowed.
- i) Immunosuppressive agents and immunosuppressive doses of systemic corticosteroids (except as stated in Section 6.5.2 regarding permitted therapies and to treat a drug-related adverse event).
- j) Co-administration of a strong UGT1A9 inhibitor (e.g. mefenamic acid, diflunisal, and niflumic acid) during regorafenib treatment should be avoided, as their influence on the steady-state exposure of regorafenib and its metabolites has not been studied.

6.5.4 Documentation of Prior and New Concomitant Therapies

All medication or vaccine (including over-the-counter or prescription medicines, vitamins, and/or herbal supplements) that may affect efficacy, toxicity or taken for any concurrent medical conditions at the time of enrollment or during the study must be recorded along with:

- a) Reason for use
- b) Dates of administration including start and end dates
- c) Dosage information including dose and frequency

The Medical Monitor should be contacted if there are any questions regarding concomitant or prior therapy.

6.5.5 Rescue Medicine

Not applicable for this study intervention

6.6 Dose Modification

Based on the known toxicity profiles of regorafenib and nivolumab, certain AEs are likely to be associated with one drug versus the other. For example, treatment emergent hypertension and HFSR are likely to be associated with regorafenib rather than nivolumab; similarly, immune-related AEs are likely to be associated with nivolumab rather than regorafenib. However, some drug-related AEs such as diarrhea, abnormal thyroid function, and fatigue are overlapping. Therefore, it is important to evaluate each AE to confirm etiology or exclude other causes in order to determine proper management of the adverse reaction and action regarding study treatment. A careful decision should be made by Investigators based on all clinical information, e.g., relatedness to study medications.

Dose modifications must be based on the maximum toxicity experienced during a cycle. The length of a cycle is 28 days (plus a potential time window, for acceptable deviation see Section 1.3 SoA). If appropriate, the Investigator may attribute each toxicity event to regorafenib or nivolumab alone or to the combination. In situations where clear attribution cannot be made to individual drugs, more conservative dose modification approach should be used for both drugs. In case of dose modifications, any efforts should be made to restart study intervention as per original schedules for regorafenib and nivolumab.

The dose modification can occur independently for the 2 drugs used if toxicity can be clearly attributed to one of the drugs. Resumption of regorafenib dosing is not dependent on resumption of nivolumab and vice versa. Treatment with individual drugs (regorafenib or nivolumab) may continue on schedule even if other drug is interrupted or permanently discontinued due to toxicity.

A cycle will be defined as 28 days regardless of interruptions.

- In case of interruption regorafenib is allowed to be re-started during the cycle within day 1 and day 21, regorafenib should not be restarted in the off week. Missed doses of regorafenib will not be replaced in the off week.
- For nivolumab dosing occurs on day 1 of every cycle
- Per protocol dose reduction or increase of nivolumab is not allowed

6.6.1 Toxicity Management, Dose Modification and Permanent Discontinuation Recommendations for Regorafenib

Table 6–2 outlines different regorafenib dose levels for the purpose of dose modification. In case a dose reduction for regorafenib is necessary, the study intervention will be administered as outlined in Table 6–2 to Table 6–6.

	days on, 7 days off)	Daily Regorafenib (21 days on, 7 days off from cycle 2 onwards if escalation if feasible)
Dose Level 0	90 mg	120 mg
Dose Level -1	60 mg	90 mg
Dose Level -2	NA	60 mg ^a

Table 6–2 Dose Levels for Regorafenib

Abbreviations: NA = Not applicable

a) If reductions are required resulting in regorafenib daily dose of less than 60 mg, then regorafenib will be permanently discontinued.

Table 6–3	Dose Modification/Dose Interruption Guide for Regorafenib-Related
Toxicities	

CTCAE Grade	Occurrences	Dose Interruption	Dose modification (when resuming treatment)
Grade 0-2 ^c	Any	No change	No change
Ore de Of	1 st and 2 nd occurrence	Hold until recovery to <g2 baselinea</g2>	Restart at same dose level or reduce 1 dose level (at the investigator's discretion)
Grade 3 ^c	3 rd occurrence	Hold until recovery to <g2 baselinea</g2>	Reduce 1 dose level or consider permanent discontinuation ^b
Grade 4 ^c	Any	-	Discontinue

Abbreviations: CTCAE = Common terminology criteria for adverse events; G = Grade; HFSR = Hand-foot skin reaction

a) Excludes alopecia, non-refractory nausea/vomiting, lymphopenia and asymptomatic laboratory abnormalities. Treatment can be resumed with Grade 2 fatigue or hypothyroidism.

- b) If reductions are required resulting in regorafenib daily dose of less than 60 mg, then regorafenib will be permanently discontinued. If toxicity returns to Grade 0-1 after dose reduction, dose reescalation is permitted in the subsequent cycle at the investigator's discretion. Participants requiring a delay of >4 weeks should discontinue regorafenib treatment. However, continuation of regorafenib may be considered if, in the investigator's opinion, the participant may continue to benefit from the regorafenib treatment, and after consultation with Sponsor.
- c) Discontinuation is required for severe bleeding necessitating urgent medical intervention, gastrointestinal perforation or fistula of any grade and posterior reversible encephalopathy syndrome (PRES) of any grade.

Page 54 of 135

Skin toxicity grade (CTCAE)	Occurrence	Dose Interruption	Dose modification (when resuming treatment)	
Grade 1	Any	Maintain dose level and institute supportive measures immediately for symptomatic relief	No Change	
	1 st occurrence	Interrupt therapy for a minimum of 7 days, until toxicity resolves to Grade 0–1	Institute supportive measures and continue same dose or consider decrease by 1 dose level	
Grade 2	No improvement within 7 d or 2 nd occurrence	Interrupt until toxicity resolves or improves to G1.	When resuming treatment, treat at reduced dose level or consider discontinuation ^a	
	3 rd occurrence	Discontinue		
	1 st occurrence	Institute supportive measures immediately. Interrupt therapy for ≥ 7 d until toxicity resolves or improves to G1.	When resuming treatment, decrease by 1 dose level	
Grade 3	2 nd occurrence	Institute supportive measures immediately. Interrupt therapy for ≥ 7 d until toxicity resolves or improves to G1.	When resuming treatment, decrease by 1 additional dose level or consider discontinuation ^a	
	3 rd occurrence	Discontinue		

Table 6–4Regorafenib Dose Modification/Dose Interruption Guidance: HFSR/Palmar-Plantar Erythrodysesthesia Syndrome

Abbreviations: CTCAE = Common terminology criteria for adverse events; G = Grade; HFSR = Hand-foot skin reaction

a) If reductions are required resulting in regorafenib daily dose of less than 60 mg, then regorafenib will be permanently discontinued. If toxicity returns to Grade 0-1 after dose reduction, dose reescalation is permitted in the subsequent cycle at the Investigator's discretion. Participants requiring a delay of >4 weeks should discontinue regorafenib treatment. However, continuation of regorafenib may be considered if, in the investigator's opinion, the participant may continue to benefit from the regorafenib treatment, and after consultation with Sponsor.

Page 55 of 135

Table 6–5	Regorafenib Dose Modification Guidance: Non-Immune Toxicities:
Hypertensic	n

CTCAE Grade	Suggested regorafenib dose interruption	Suggested regorafenib dose modification
Specific guidance for	or HYPERTENSION	
Grade 1	No change.	Consider increased BP monitoring
Grade 2	If symptomatic, hold until symptoms resolve and diastolic BP ≤ 90 mmHg. Treat with anti-hypertensive medications	At restart, continue at the same dose level
	Hold until diastolic BP ≤ 90 mm Hg, and if symptomatic, until symptoms resolve. Treat with additional anti-hypertensive medications	At restart, continue at the same dose level.
Grade 3	If BP is not controlled with the addition of new or more intensive therapy.	Reduce by 1 dose level
	If G3 hypertension recurs despite dose reduction and optimal antihypertensive therapy	Reduce another dose level or consider discontinuation ^a
Grade 4 ^b	Discontinue	

Abbreviations: BP = Blood pressure; CTCAE = Common terminology criteria for adverse events; G = Grade; Hg = Mercury

a) If reductions are required resulting in regorafenib daily dose of less than 60 mg, then regorafenib will be permanently discontinued. If toxicity returns to Grade 0-1 after dose reduction, dose reescalation is permitted in the subsequent cycle at the investigator's discretion. Regorafenib cannot be interrupted for more than 28 consecutive days including the drug holidays. However, continuation of regorafenib may be considered if, in the investigator's opinion, the participant may continue to benefit from the regorafenib treatment, and after consultation with Sponsor.

b) This includes hypertensive crisis per CTCAE v 5.

Table 6–6	Dose Modification/Dose Interruption Guide for Regorafenib-related
Toxicities: L	iver Function Test Increases Related to Regorafenib ^a

Increases in AST/ALT/Bilirubin	Occurrence	Dose Interruption	Dose Modification (when resuming treatment)
(from baseline within normal limits) AST and/or ALT < 3 times ULN or total bilirubin < 1.5 times ULN	Any	Continue dosing	No Change
(from baseline AST/ALT more than 1 and up to 3 times ULN) AST or ALT more than 3 and up to 5 times the ULN	Any	Continue dosing	No Change
(from baseline within normal limits) AST or ALT more than 3 and up to 5 times the ULN or total bilirubin more	1 st occurrence	Delay dosing until return to Grade ≤ 1 or baseline	Reduce 1 dose level ^b
than 1.5 and up to 3 times the ULN	Re-occurrence	Discontinue	
(from baseline any grade) AST or ALT more than 5 times the ULN or total bilirubin more than 3 times the ULN	1 st occurrence	Delay dosing until return to Grade ≤ 1 or baseline	If the potential to reinitiate regorafenib is considered to outweigh the risk of hepatotoxicity: reduce 1 dose level
	Re-occurrence	Discontinue	
(from baseline any grade) AST and/or ALT > 20 x ULN	Any	Discontinue	

Page 56 of 135

Increases in AST/ALT/Bilirubin	Occurrence	Dose Interruption	Dose Modification (when resuming treatment)
AST and/or ALT > 3 x ULN with concurrent bilirubin > 2 x ULN	Any	Discontinue°	

Abbreviations: ALT=Alanine aminotransferase; AST=Aspartate aminotransferase; ULN = Upper limit of normal
 a) For any of the events listed above (dose interruption or modification): monitor liver function tests weekly or more frequently until recovery to baseline or stabilization

 b) If all values remain stable for 2 full cycles, dose re-escalation may be considered at the discretion of the Investigator. After re-escalation AST, ALT, bilirubin should be checked 2×/week for 2 weeks, followed by weekly assessments for at least 4 weeks.

c) Exception: participants with Gilbert's syndrome who develop elevated transaminases should be managed as per the above outlined recommendations for the respective observed elevation of ALT and/or AST.

6.6.2 Toxicity Management, Dose Modification and Permanent Discontinuation Recommendations for Nivolumab

There will be no dose reductions for nivolumab. Recommendations for nivolumab delay and discontinuation are provided (Table 6–7) when the Investigator attributes toxicity event to nivolumab either alone or in combination with regorafenib. In situations where clear attribution cannot be made to an individual drug (regorafenib or nivolumab), a more conservative dose modification approach should be used for both drugs (Section 6.6).

Resumption of nivolumab dosing is not dependent on resumption of regorafenib and vice versa. Treatment with individual drugs (regorafenib or nivolumab) may continue on schedule even if other drug is interrupted or permanently discontinued due to toxicity. Further details regarding resumption of nivolumab are specified in Section 6.6.2.1.

AEs (both non-serious and serious) associated with nivolumab exposure may represent an immunologic etiology. These AEs may occur shortly after the first dose or several months after the last dose of treatment. Therefore, early recognition and initiation of treatment is critical to reduce complications (Section 6.6.2.2).

Interrupt or slow the rate of infusion in participants with mild or moderate (Grade 1-2) infusion reactions. Discontinue nivolumab in participants with severe or life-threatening infusion reactions (Grade 3-4). Additional information is in Section 6.6.2.3.

Page 57 of 135

Adverse Reaction	Severity (CTCAE v5)	Dose Modification
	Grade 2 diarrhea or colitis	Withhold dose ^b
	Grade 3 diarrhea or colitis	Withhold dose ^b
Colitis	Grade 4 diarrhea or colitis	Permanently
	Clade 4 diamiea di contis	discontinue
	Grade 2 pneumonitis	Withhold dose ^b
Pneumonitis	Grade 3 or 4 pneumonitis	Permanently
- nodinomilo		discontinue
Hepatitis/non-hepatocellular	AST or ALT more than 3 and up to 5 times the ULN or total bilirubin more than 1.5 and up to 3 times the ULN	Withhold dose ^b
carcinoma	AST or ALT more than 5 times the ULN or total bilirubin more than 3 times the ULN	Permanently discontinue ^c
Hypophysitis/ Hypopituitarism	Grade 1-3 hypophysitis that is also associated with corresponding abnormal lab and/or pituitary scan	Withhold dose ^b
	Grade 4	Permanently
		discontinue
	Grade 2 or 3	Withhold dose ^d
Hyperthyroidism or Hypothyroidism	Grade 4	Withhold dose or
		permanently
	Crade 2 adrenal insufficiency	discontinue Withhold dose ^b
Adronal Insufficiency	Grade 2 adrenal insufficiency	
Adrenal Insufficiency	Grade 3 or 4 adrenal insufficiency	Permanently discontinue ^e
	Grade 2 or 3 hyperglycemia	Withhold dose ^b
Hyperglycemia	requiring initiation or change in daily management	
, , , , , , , , , , , , , , , , , , ,	Grade 4 hyperglycemia	Permanently discontinue
Nephritis and Renal Dysfunction	Serum creatinine more than 1.5 and up to 6 times the ULN	Withhold dose ^b
Replinus and Renai Dysidiction	Serum creatinine more than 6 times	Permanently
	the ULN	discontinue
Skin	Grade 2 rash covering >30% BSA or 3 rash or suspected SJS, TEN or DRESS	Withhold dose ^b
	Grade 4 rash or confirmed SJS,	Permanently
	TEN or DRESS	discontinue
Myasthenia gravis, Guillain-Barre syndrome, treatment-related myelitis, or encephalitis	Any grade	Permanently discontinue
Neurological adverse reaction (other than Guillain-Barre syndrome,	Grade 2	Withhold dose ^b
myasthenia gravis, encephalitis, or myelitis)	Grade 3 or 4	Permanently discontinue
Other	Other Grade 3 adverse reaction: First occurrence Recurrence of same Grade 3 AR	Withhold dose ^b Permanently discontinue

Table 6–7 Recommended Dose Modification for Nivolumab^a

Life-threatening or Grade 4 AR	Permanently discontinue
Grade 2 myocarditis	Withhold dose ^b
Grade 3 or higher myocarditis	Permanently discontinue
Requirement for 10 mg per day or greater prednisone or equivalent for more than 12 weeks	Permanently discontinue
Persistent Grade 2 or 3 ARs lasting 12 weeks or longer	Permanently discontinue

Abbreviations: ALT = Alanine aminotransferase; AR = Adverse reaction; AST = Aspartate aminotransferase; NCI CTCAE = National Cancer Institute Common Terminology Criteria for Adverse Events; SJS = Stevens-Johnson syndrome; TEN = Toxic epidermal necrolysis; DRESS = Drug Reaction with Eosinophilia and Systemic Symptoms; ULN = Upper limit of normal

- a) For additional management recommendations, please see Appendix 9: Guidance for Management of Immune-Related Adverse Events Section 10.9.
- b) Resume treatment when adverse reaction improves to Grade 0 or 1 (see further details in Section 6.6.2.1).
- c) In most cases of AST or ALT > 5 x ULN, study treatment will be permanently discontinued. If the investigator determines a possible favorable benefit/risk ratio that warrants continuation of study treatment, a discussion between the investigator and the Medical Monitor/ designee must occur and approval from Medical Monitor prior to resuming therapy.
- d) Dosing may resume if endocrinopathy resolves to be asymptomatic, or is adequately controlled with only physiologic hormone replacement or other medical management.
- e) If adrenal insufficiency resolves or is adequately controlled with physiologic hormone replacement, participant may not require discontinuation of study drug. Mandatory discussion with and approval from the Medical Monitor needed prior to resuming therapy.

Nivolumab Treatment – Permanent Discontinuation

In addition to nivolumab treatment discontinuation specified in Table 6–7, the following criteria of discontinuation are as follow:

- a) Patients who complete 24 infusions of nivolumab (after approximately 2 years of treatment)
- b) In the scenario when AST or ALT elevation fulfills the criteria of discontinuation and the investigator judges there is a possible favorable benefit/risk profile that warrants continuation of nivolumab treatment, a discussion between the investigator and the Sponsor must occur.
- c) Any event that leads to delay in dosing lasting >10 weeks from the previous dose requires discontinuation, with the following exceptions:
 - Dosing delays to allow for prolonged steroid tapers to manage drug-related adverse events are allowed.
 - Dosing delays lasting > 10 weeks from the previous dose that occur for non-drug-related reasons may be allowed if approved by the Sponsor.
- d) Any adverse event, laboratory abnormality, or intercurrent illness which, in the judgment of the Investigator, presents a substantial clinical risk to the participant with continued nivolumab dosing.

CONFIDENTIAL

Prior to re-initiating treatment in a participant with a dosing delay lasting > 10 weeks, the Sponsor must be consulted. Tumor assessments should continue as per protocol even if dosing is delayed.

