27 JAN 2021

Page 17 of 135

					Tr	reatme	nt pe	riod							Long-	
Procedure	Screer	Screening		Cycle1				Cycle	2	Cycle ≥3	EoT visit	Active FU ^a			term FU	Comments
	within 28 d prior to first dose	within 7 d prior to first dose	D 1	D 8	D15	D22	D1	D8	D15	D1	within 14 d after permanent study treatment discontinuation	Safety FU visit 30 d after permanent study treatment discontinuation	Safety FU visit 100 d after LD for nivolumab ^a	Efficacy FU visit (between EoT and confirmed radiological PD)	every 3 months (phone call)	
acceptable deviation (days)				±2d ±2d ±3d					± 3 d		+ 7 d	+ 14 d	± 14 d	± 14 d		
Urine analysis by dipstick ^g		х	х				х			х	х	х	х			Table 10–1
Thyroid function testing ^g		х					х			х	Х	х	Х			Table 10–1
12-lead ECG ^h	Х		Х				Х			х	Х	х	Х			Section 8.2.3
Vital signs (including weight)		х	х				Х			х	х	х	х			Section 8.2.2
Efficacy																
Tumor assessments – (CT/MRI) ⁱ	х									x	X ^{a,i}	X ^{a,i}	X ^{a,i}	X ^{a,i}		Section 8.1
Bone scan ⁱ	х				←====				===== If	indicated, s	ee section 8.1 ===				Section 8.1	
Brain scan (MRI/CT) ⁱ	х				←====		=====		===== If	indicated, s	ee section 8.1 ===		→			Section 8.1
Survival status															х	
1st subsequent anti-cancer treatment											х	х	х	x	x	
Study intervention administration																
Study treatment: Nivolumab ⁱ			х				х			Х						Section 6.1
Study treatment: Regorafenib ^j			←========→ 3 weeks on/ 1 week off							=→						Section 6.1

Clinical Study Protocol Global Amendment 1 BAY 73-4506/ 21136

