4.1.2 Treatment Phase

The start of the treatment period is defined by the first administration of study treatment. The length of a cycle is 28 days (plus a potential time window, for acceptable deviation see Section 1.3 SoA). Participants will be treated with nivolumab intravenously given on Day 1 and regorafenib orally every day for 3 weeks of a 4 week cycle. Nivolumab will be administered as a flat dose of 480 mg using a 30 min i.v. infusion Q4W. Regorafenib will be given at a starting dose of 90 mg for 21 days of every 28-day cycle (i.e., 21 days on, 7 days off). If the starting dose of 90 mg daily is well tolerated (absence of any grade rash/hand foot skin reaction (HFSR) or other Grade 2 or higher clinically significant toxicity) the dose can be escalated to 120 mg orally daily anytime after Cycle 1, starting with Cycle 2 Day 1. The Sponsor will be immediately informed, if the Investigator decides not to escalate the dose to 120 mg on C2D1 despite meeting the criteria.

Dose modification guidelines for dose reduction in case of toxicity are detailed in Section 6.6. Treatment with individual drugs (regorafenib or nivolumab) may continue on schedule even if the other drug is interrupted or permanently discontinued due to toxicity.

Participants who complete 24 infusions of nivolumab (after approximately 2 years of treatment) need to discontinue treatment with nivolumab. Regorafenib monotherapy treatment can be continued beyond 2 years until discontinuation criteria are met.

During the study, participants will undergo evaluations for safety, efficacy, pharmacokinetics and tissue and blood for biomarker will be collected.

Response will be assessed by imaging and participants may continue treatment until confirmation of disease progression per response evaluation criteria in solid tumors for trials testing immunotherapeutics (iRECIST; Section 10.6.2) or per immune response assessment in neuro-oncology (iRANO; Section 10.6.4), unacceptable toxicity or any other protocol defined criterion for withdrawal occurs. See Section 8.1 for further details on treatment continuation and tumor assessments beyond progression per RECIST 1.1 or RANO criteria. Primary endpoint of the study for all cohorts is ORR as measured by RECIST 1.1 or RANO for GBM/AA as determined by the investigator. For GBM/AA tumor assessment per RANO will

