6.1 Study Intervention(s) Administered

Table 6–1 Administration of Study Intervention

Study Intervention	Regorafenib	Nivolumab	
Туре	small molecule drug (MKI)	monoclonal antibody (mAB), biologic	
Dose Formulation	tablet	solution for infusion	
Unit Dose Strengths	30 mg / tablet	100 mg / 10 mL vial (10 mg/mL)	
Dosage Levels	3x 30 mg tablets every day (q.d.) for 21 days of every 28-day cycle (21 days on, 7 days off) as a starting dose of 90 mg. If the starting dose is well tolerated dose should be escalated to 120 mg (4x30 mg tablets) starting with C2D1.	480 mg (5x100 mg / 10 mL vials) on D1 of each cycle	
Route of Administration	oral	i.v. infusion	
Use	experimental	experimental	
IMP and NIMP	IMP	IMP	
Sourcing	Regorafenib will be provided centrally by the Sponsor.	Nivolumab will be provided centrally by the Sponsor.	
Packaging and Labeling	Regorafenib is available in high density polyethylene bottles with a white child resistant closure and induction seal. The packaging configuration is 21 tablets Regorafenib 30 mg and a 3 g desiccant per bottle. The bottles will be labeled as required per country requirement.	Nivolumab will be provided in glass injection vial. Each glass injection vial will be labeled as required per country requirement.	
Current/Former Name(s) or Alias (es)	Stivarga / BAY 73-4506	Opdivo®	

Abbreviations: IMP = Investigational medicinal product; i.v. = Intravenous; mAB = Monoclonal antibody; MKI = Multikinase inhibitor; NIMP = Non-investigational medicinal product

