8.2.1 Physical Examinations

For physical examinations please refer to Section 1.3 (SoA).

Full physical examination includes, at a minimum, assessments of the cardiovascular, respiratory, gastrointestinal and neurological systems and of skin status. Height will be measured at screening only.

A limited physical exam is based on symptom-directed findings or as clinically indicated. New clinically significant abnormal findings should be recorded as AEs. Investigators should pay special attention to clinical signs related to previous serious illnesses.

For GBM and AA, neurologic examinations (via Neurologic Assessment in Neuro-Oncology (NANO) Scale) in addition to the physical examinations will be performed that will include assessments of mental status and neurologic functions (motor and sensory systems, cranial nerves, reflexes, or other symptom-directed findings as clinically indicated).

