8.2.2 Vital Signs

Body temperature, heart rate, blood pressure, height (only at screening) and weight will be assessed.

BP and heart rate measurements should be preceded by at least 5 min of rest for the participant in a quiet setting without distractions (e.g., television, cell phones).

When vital signs measurements and ECG measurements are scheduled at the same time point, ECG must be obtained before vital signs.

When blood pressure (BP) measurement and PK sample collection are scheduled at the same time point, participant's blood pressure must be measured before collection of PK sample.

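### No blood pressure reading is scheduled on Days 2-28 of any treatment cycle, so the expected C2D1 escalation to 120 mg and the hypertension dose rules have no scheduled reading from the dosing period behind them

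*Protocol*

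**What the plan says.** **When blood pressure is measured.** Protocol Section 8.2.2 lists it among the vital signs: "Body temperature, heart rate, blood pressure, height (only at screening) and weight will be assessed". It has no row of its own in Table 1-2 (Section 1.3), and Section 8.2 refers to that table for the timing of all safety assessments. The vital-signs row is marked at screening (within 7 days of first dose), C1D1, C2D1, Day 1 of Cycle 3 onward, EoT, and the 30-day and 100-day safety visits. It is blank at C1 D8, D15, D22 and C2 D8, D15. Those five visits carry a limited examination, which Section 8.2.1 describes so: "A limited physical exam is based on symptom-directed findings or as clinically indicated".

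**How toxicity drives the dose.** Section 6.6 sets the rule: "Dose modifications must be based on the maximum toxicity experienced during a cycle". For Grade 3 hypertension, Table 6-5 says "Hold until diastolic BP ≤ 90 mm Hg, and if symptomatic, until symptoms resolve", so the hold applies with or without symptoms. At Grade 1 the table only suggests considering more frequent checks.

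**Escalation.** Section 4.1.2 defines good tolerance as no rash or hand-foot skin reaction of any grade and no "other Grade 2 or higher clinically significant toxicity) the dose can be escalated to 120 mg orally daily anytime after Cycle 1". It adds: "The Sponsor will be immediately informed, if the Investigator decides not to escalate the dose to 120 mg on C2D1 despite meeting the criteria". Table 6-1 is more directive: "If the starting dose is well tolerated dose should be escalated to 120 mg (4x30 mg tablets) starting with C2D1".

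**The concern.** The dose rules act on the worst toxicity in a cycle, but the schedule measures blood pressure only at the cycle's start. From Cycle 2 that reading comes at the end of the off week. Hypertension without symptoms is found by measurement, and a symptom-led examination cannot be relied on to prompt one.

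The protocol expects this toxicity. Section 6.6 names hypertension as likely to be due to regorafenib. Section 2.3 reports Grade 3 or higher treatment-related hypertension in 14% of patients with liver cancer given regorafenib plus pembrolizumab. Section 4.3 lists Grade 3 or higher hypertension in the Phase 1b trial of regorafenib plus nivolumab, although the count is lost in the text.

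Two things are at stake. A participant whose pressure rises on 90 mg may go untreated, and may then be moved to 120 mg because nothing scheduled shows poor tolerance. After escalation at C2D1, the first scheduled reading that follows a course at 120 mg is C3D1, again after an off week.

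**Working it through.** The plan gives no figure to reproduce. The check is a column-by-column reading of Table 1-2 with simple day counts.

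**Inputs**
- Regorafenib dosing: Days 1-21 on, Days 22-28 off (Section 4.1.2).
- Visit windows: ±2 days in Cycles 1 and 2, ±3 days from Cycle 3 (Table 1-2).
- Liver tests: AST, ALT and bilirubin are in both chemistry panels (Table 10-1). Table 1-2 marks the expanded panel at C1 D15 and C2 D15, and the limited panel at C1 D8, C1 D22 and C2 D8.
- Regorafenib taken under site supervision: D1, D8 and D15 of Cycle 1, and D1 and D15 of Cycle 2 (Section 6.4).

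**Step 1. Marks at the mid-cycle visits**

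| Visit | Dosing day? | Limited examination | Liver tests | Vital signs |
|---|---|---|---|---|
| C1 D8 | yes | yes | yes | no |
| C1 D15 | yes | yes | yes | no |
| C1 D22 | no (Day 21 + 1) | yes | yes | no |
| C2 D8 | yes | yes | yes | no |
| C2 D15 | yes | yes | yes | no |

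Liver tests: 5. Blood pressure: 0. From Cycle 3 only Day 1 visits exist, so the count on Days 2-28 is 0 there too. The liver rules in Table 6-6 thus have scheduled data from the dosing period, while the hypertension rules in Table 6-5 have none.

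**Step 2. Distance of the Day 1 reading from the last dose**
- C2D1 is Day 29 of Cycle 1: 29 − 21 = 8 days after the last planned dose, with 7 dose-free days between. With ±2 days the range is 6 to 10.
- From Cycle 3 it is again 8 days; with ±3 days, 5 to 11.

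The protocol does not say whether Day 1 vital signs come before or after that day's dose. If after, the reading would reflect one dose of the new course and would still not cover Days 2-21.

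**Step 3. Effect of measuring at the existing visits**
- Added readings: 3 in Cycle 1 + 2 in Cycle 2 = 5, of which 4 fall on dosing days.
- Readings between C1D1 and the C2D1 visit rise from 0 to 3, of which 2 fall on dosing days.

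**Step 4. Volume**
- Stage 1: 3 × 9 + 14 + 2 × 17 = 75 participants; 75 × 5 = 375 readings.
- Whole trial at its ceiling: 200 × 5 = 1,000 readings.

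**The case against.** The schedule and the arithmetic are not in dispute. The case against concerns consequence.

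- **There is a reading at C2D1.** Blood pressure, full examination, ECG and laboratory tests are all due there, so hypertension that persists is caught. The dose-free week may also not be free of drug effect: Section 6.5.1.2 reports about 44% higher SN-38 exposure when irinotecan followed regorafenib after a 5-day break. This stands in part. The documents give neither a half-life nor the time blood pressure takes to fall, so *dose-free* is the safe term. The cases at risk are those that rise during dosing, go unnoticed and settle by C2D1.
- **Asymptomatic Grade 2 is not clearly a bar.** The criterion requires clinical significance, and Table 6-5 calls for antihypertensive treatment there without a hold. That is fair, but the treatment also depends on detection, and Grade 3 does trigger a hold without symptoms.
- **Escalation may be optional.** Sections 4.1.2 and 6 say the dose *can* be raised. Even so, the wording of Table 6-1 and the duty to tell the Sponsor when an eligible participant is not escalated make it the expected course.
- **Investigators may check more often.** Section 8.2 allows extra assessments and asks for monitoring to local standards after a dose modification, adverse events are reviewed throughout, and poorly controlled hypertension is excluded at entry. None of this requires a Cycle 1 reading before escalation. The Investigator's Brochures, which may say more, are not supplied.
- **No endpoint is shown to be affected.** Correct. This is a point of participant safety and dose assignment.

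**Conclusion.** The concern holds. While treatment continues, no blood pressure reading is scheduled on Days 2-28 of any cycle. The escalation decision at C2D1 rests on a single reading 6 to 10 days after the last planned dose, and detecting asymptomatic hypertension during dosing is left to the investigator's discretion. The rule on maximum toxicity in a cycle therefore cannot be applied to hypertension from scheduled data.

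This concerns scheduled readings only and assumes dosing and visits run to plan. An EoT visit can fall on any day of a cycle, but by then treatment has stopped. The number of missed cases cannot be estimated from the documents. Nothing is concluded about the vital-signs summary: SAP v3.0 refers it to SAP v2.0, which is not supplied. The change should be made because it protects participants against an expected toxicity at little cost.

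**What to change.** 1. In the vital-signs row of Table 1-2, mark blood pressure at C1 D8, D15 and D22 and at C2 D8 and D15.
2. In Sections 4.1.2 and 6, require the Cycle 1 readings to be reviewed before the C2D1 decision on 120 mg.

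This needs a small amendment to the Schedule of Activities and no new visit. At three of the five visits (C1 D8, C1 D15, C2 D15) regorafenib is already taken under supervision. Each reading needs at least 5 minutes of rest (Section 8.2.2), so at least 5 × 5 = 25 minutes of rest per participant over two cycles.

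Cycle 3 onward stays uncovered, including for a participant first escalated then. Readings during dosing in those cycles would need home measurement or extra visits, which are not proposed here.
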